15.2 FOLLOW-UP FORMS

The follow-up part of the case record forms contains one normal follow-up form to complete each year. Minor complaints or complications can be noted in these forms. Complaints that are more serious or complications necessitating hospital intake, but not related to cancer should be noted in the form for events not related to cancer. In case of recurrences, the recurrence form and the recurrence follow-up form should be completed.

16 RECURRENT DISEASE

Recurrences should be reported by fax to the coordinating center within 2 weeks after detection.

16.1 DEFINITIONS OF RECURRENT DISEASE

Evidence of recurrent disease is accepted when one of the following criteria is present:

- locoregional macroscopic tumor assessed by colono- or proctoscopy or barium enema
- positive histology or cytology of adenocarcinoma, compatible with the primary tumor in any location
- liver metastases on ultrasound, CT-scan or MRI
- lung metastases on chest radiography, CT-scan or MRI
- bone metastases on radiography or bone scintigraphy
- death with cancer

16.2 DEFINITIONS OF LOCOREGIONAL RECURRENCE

- rectal exam positive for rectal cancer
- positive MRI or CT
- positive cytology or histology of adenocarcinoma

16.3 TREATMENT OF RECURRENT DISEASE

Treatment of recurrent disease should be according to local standards as long as patients in each treatment group are treated according to the same protocol. Protocols should be known to the main coordinating center. Any changes in these protocols during the study period should be reported to and approved by the protocol committee. Treatment should be noted in the recurrence follow-up form.

16.4 FOLLOW-UP OF RECURRENT DISEASE

Follow-up of patients with recurrent disease should continue at least 3 years after diagnosis of recurrence or until death. Recurrences and their treatment should be noted in the recurrence form and the recurrence follow-up form.

17 DATA COLLECTION

All medical, quality of life and cost data will be collected by the main coordinating center, Erasmus MC Rotterdam, The Netherlands. Data collection will be facilitated by case record forms for the perioperative period including data on pathology and follow-up.

For privacy of patients, no hospital patient identification numbers will be revealed to the coordinating center. All patient data are coded and identified by means of a randomization number. The local investigator will have a decoding list with randomization numbers and hospital patient identification numbers of his patients in the investigator site file (see appendix).

At each trial operation, the code(s) of the performing surgeon(s) should be noted in the case record form. For this purpose, surgeons performing laparoscopic or open rectal resections in the trial must be coded and a list of these surgeons with their corresponding codes should be kept in the investigator site file (see appendix).

All patients who are considered for operative treatment of rectal carcinoma should be registered, including those who refuse randomization and those who do not meet inclusion criteria. Brief details of the reasons why patients are not randomized or excluded should be given. The number of patients operated in each center for rectal cancer will be registered.

17.1 DATA COLLECTED AT RANDOMIZATION

At randomization, the clinician will be asked to give the following information through the internet:

- eligibility criteria fulfilled?
- randomizing physician / surgeon
- hospital (+fax number)
- kind of operation planned
- sex of patient
- date of birth
- clinical TNM stage

17.2 DATA COLLECTED DURING PRE-OPERATIVE PERIOD

- ASA class
- length and weight
- number of previous abdominal operations
- date of diagnosis
- location of tumor
- proposed type of resection
- previous radiotherapy of the pelvis
- preoperative radiotherapy

17.3 DATA COLLECTED DURING OPERATION

- code(s) of surgeon(s)
- date of surgery
- type and level of resection
- use of ureter stent
- presence of radiation damage
- presence of liver or peritoneal metastases
- invasion of adjacent organ(s)
- degree of autonomic nerve preservation
- location and length of incision
- type and method of performing anastomosis
- blood loss (ml)
- "skin to skin" time
- intra operative complications
- wound protection / specimen protection used
- steps of operation accomplished laparoscopically
- reasons for conversion to conventional procedure

17.4 DATA COLLECTED DURING POST-OPERATIVE PERIOD

The post-operative period is defined as the period starting when the patient is leaving the operating theatre and ending 8 weeks after that. The day of operation is day 0.

- post-operative day with fluid intake > 1000 ml resumed
- post-operative day with passage of first stool
- day of discharge from hospital
- complications including death and cause of death and number of re-interventions and reasons of further abdominal surgery
- reason and duration of possible readmission in hospital within 8 weeks after surgery
- analgesic requirement during the first three days

17.5 DATA COLLECTED AT PATHOLOGIC ANATOMICAL EXAMINATION

- macroscopic description
- histology
- extent of local invasion
- circumferential margin
- distal margin
- peritoneal spread
- metastatic spread
- synchronous colon pathology
- pTNM (see appendix)

17.6 DATA COLLECTED DURING FOLLOW-UP PERIOD

Once a year the following data will be collected:

- date of visit
- adjuvant therapy
- details on recurrence, including date and method of diagnosis, site of recurrence and treatment consequences
- details on possible complications
- date of death and cause of death

18 SUB-STUDIES

18.1 QUALITY OF LIFE

Quality of life will be assessed by, at least:

- EuroQOL 5-D, scored no more than 5 days pre-operatively and on 4 weeks, 6 months, 12 months and 24 months postoperatively
- EORTC QLQ-CR38, scored no more than 5 days pre-operatively and on 4 weeks, 6 months, 12 months and 24 months postoperatively
- EORTC QLQ-C30, scored no more than 5 days pre-operatively and on 4 weeks, 6 months, 12 months and 24 months postoperatively
- Subset of EORTC QLQ-P25 on sexual and bladder function, scored no more than 5 days pre-operatively and on 4 weeks, 6 months, 12 months and 24 months and postoperatively

In addition, the following questionnaires **may** be used and **are** used as part of a national Dutch study:

- VAS for pain and nausea, scored no more than 5 days pre-operatively and on days 1, 3 and 7 days postoperatively
- Health and care questionnaires, scored no more than 5 days pre-operatively and every week for 8 weeks postoperatively

18.2 COSTS

Direct and indirect medical cost driving medical events will be assessed for the entire trial population based on data from the case record forms from the operation and the follow up period and also based on data from the Quality of Life substudy. The method has been described earlier (ref: Björholt I, Janson M, Jönsson B, Haglund E. Principles for the Design of the Economic Evaluation of COLOR II: an International Clinical trial in Surgery Comparing Laparoscopic and Open surgery in Rectal Cancer. *Int J Technol Assess Health Care* 2006;22(1):130-5.) Thereafter medical costs will be applied on a national basis for national health economy analyses.

18.3 OTHER SUBSTUDIES

Lateral substudies can be performed when measured variables are not part of primary or secondary endpoints of the COLOR II. The board of governors must be informed and must confirm that there is no conflict of interest with the COLOR II trial.

19 STATISTICAL CONSIDERATIONS

19.1 SAMPLE SIZE AND STATISTICAL ANALYSIS

Locoregional cancer recurrence rate of operated patients with cancer stages <IV after 3 years is currently about 10 %. The primary objective of the study is to show that laparoscopic surgery does not lead to an increased locoregional recurrence rate. Equivalence of both treatments is considered to be shown if the resulting two-sided 95% confidence limits of the difference in 3-yrs locoregional recurrence rates excludes a difference greater than 5%. At a randomization ratio of 2:1, and assuming a recurrence rate of 10% in each group, 850 laparoscopic patients and 425 open patients are required to have a power of 80% for this study.

All analyses will be carried out on an "intention to treat" basis: patients, whose randomized laparoscopic operation was converted to an open resection, will be analyzed in the laparoscopic group.

Eight weeks operative mortality, pathological resection margins and complication rates will be compared using the Chi-square test. Locoregional recurrence rate, disease free survival and overall survival will be compared between the two procedures using log-rank statistic, adjusted for center. Exploratory analysis of the prognostic effects of various baseline data will be done using multivariate Cox-regression. Analysis of the primary endpoint will be performed 1.5 - 2 years after inclusion of all patients.

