3.4 STATISTICS & RANDOMIZATION

Using log rank statistics with a power of 80 % and a type I error of 5%, 1275 patients are needed to detect a difference between both treatment arms of 5% in locoregional recurrence rate 3 years postoperatively, assuming a 10% recurrence rate in the open group. Randomization will be 2:1, laparoscopic versus open resection respectively. Analyses will be on "intention to treat" basis. Randomization is stratified for each participating center, planned procedure, radiotherapy and sex.

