4.3 LAPAROSCOPIC SURGERY FOR COLORECTAL CANCER

Recently, Lacy et al published the first long-term results of a randomized trial comparing laparoscopic colectomy versus open colectomy for the treatment of colonic cancer. This study demonstrated improved 3-year cancer related survival following laparoscopic surgery compared to open surgery (91% vs 74% respectively). The observed benefit could mainly be attributed to lower tumor recurrence and a longer overall survival of patients with stage III colonic cancer [2]. The authors concluded that laparoscopic colectomy is preferred to open colectomy in patients with colonic cancer. Results of this study have to be interpreted with great care because it represents a single institution experience with a relative small number of patients. Results of large multi-center trials will have to be awaited. Interim analysis of these randomized trials have not shown significant differences of recurrence rate so far, as none of the trials have ceased including new patients for this reason.

Laparoscopic colorectal surgery was first reported in 1991 by Jacobs et al [3]. In spite of the technical complexity and initial high financial costs of laparoscopic colorectal surgery, feasibility to use laparoscopic techniques for almost the entire spectrum of colorectal surgery has been established [4-10]. In a registry, supported by the American Society of Colon & Rectal Surgeons and the American College of Surgeons, of 453 laparoscopic resections for colorectal cancer, subjective violation of cancer principles occurred in only 1 percent of patients [11].

However, first reports on abdominal wall metastases after laparoscopic resection of colorectal cancers have caused major concern [12]. Comparison of the incidences of abdominal wall metastases after open and laparoscopic colectomy is not possible because true incidence rates are unknown. Incidences of abdominal wall metastases vary from 0.69 % to 16.6 % [13-16] following open resection for colorectal cancer and from 0.6 % to 21 % [11, 12, 17, 18] following laparoscopic resection of colorectal cancer. Review of laparoscopic resections for colorectal cancer has shown the majority of reported abdominal wall metastases to occur in patients with loco-regionally advanced disease or diffuse peritoneal carcinomatosis [8, 19]. Recent reports on laparoscopic colon resection for malignancies do not show an increased incidence of abdominal wall

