7 ETHICS

The trial must be approved by the appropriate ethics committee of each participating institution prior to its entry into the study. Eligible patients should be informed in person by the treating surgeon and receive written information about the trial in their own language. Informed consent should be obtained from each patient according to the guidelines of the local ethical committee, prior to randomization into the study. Patients remain free to withdraw at will at any time from the study without giving reasons.

To guarantee optimal treatment for patients in both treatment arms, interim analyses will be performed to compare survival and recurrence in both treatment arms. If differences of survival or recurrence rates are significant, accrual of patients will be stopped.

To assess the feasibility of laparoscopic rectal cancer resection, a phase II trial will precede the accrual of patients in this trial.

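### The 1275 patients in sections 19.1 and 3.4 contain no allowance for loss: the stated 80% power holds only if every randomized patient's 3-year locoregional status is known

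*Protocol*

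**What the plan says.** Section 19.1 sets the criterion for the primary claim: it is met if "the resulting two-sided 95% confidence limits of the difference in 3-yrs locoregional recurrence rates excludes a difference greater than 5" percentage points. The planning inputs follow: "At a randomization ratio of 2:1, and assuming a recurrence rate of 10% in each group". The result is that "850 laparoscopic patients and 425 open patients are required to have a power of 80% for this study".

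Section 3.4 gives the same total as the size of the trial: "1275 patients are needed to detect a difference between both treatment arms of 5% in locoregional recurrence rate 3 years postoperatively". It describes the calculation differently from 19.1. Only the total matters here.

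Neither section mentions attrition, although other parts of the protocol allow for patients leaving the analysis:

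- Section 7: "Patients remain free to withdraw at will at any time from the study without giving reasons".
- Section 9.3 lists two exclusions after randomization (no adenocarcinoma; invasion of uterus or vagina found at operation).
- Section 17.6 collects the date and cause of death during follow-up.

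No expected rate is given for any of these. Section 19.1 compares locoregional recurrence by a log-rank test adjusted for center.

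**The concern.** The sample size formula counts patients whose 3-year outcome is known. The protocol uses its result as the number to enrol. These are the same number only if nobody is lost.

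Section 15.1 schedules one examination a year and pelvic CT or MRI at three years to exclude local recurrence. A patient who withdraws before that scan lacks the assessment on which the 3-year status largely rests. Each such loss widens the confidence interval for the 3-year difference, and the width of that interval decides the primary claim. If the two procedures are truly equal, the trial then fails to exclude a 5-point difference more often than the planned one time in five.

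**Working it through.** **Inputs, all from section 19.1.** Recurrence 10% in each arm, so p(1−p) = 0.09 and the true difference is 0; limit 0.05; two-sided 95% interval (z = 1.96); power 80% (z = 0.8416); 2:1 allocation, 850 + 425.

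**1. Reproduce the printed number.**

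n(open) = (1.96 + 0.8416)² × 0.09 × (1 + 1/2) / 0.05² = 423.8, so 424; n(laparoscopic) = 848; total 1272.

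Power at 850 + 425: SE = √[0.09 × (1/850 + 1/425)] = 0.01782, and Φ(0.05/0.01782 − 1.96) = 80.1%.

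The plan's figure is reproduced. It exceeds the bare formula by 1275 − 1272 = 3 patients, so no inflation for loss is included.

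**2. Lost patients contribute nothing.** The loss d is an assumption and is equal in both arms.

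SE = √[0.09/(850(1−d)) + 0.09/(425(1−d))]; power = Φ(0.05/SE − 1.96).

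**3. Lost patients are censored part-way.** Loss occurs at a constant rate over 3 years and reaches d by year 3. Recurrence also has a constant hazard, reaching 10% at year 3. With λ = −ln(0.9)/3 and c = −ln(1−d)/3, the large-sample Kaplan-Meier (Greenwood) variance per patient is

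V = 0.9² × λ/(λ + c) × [exp(3(λ + c)) − 1],

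which replaces 0.09 in the SE with the full 850 + 425. At d = 10%, c equals λ, so V = 0.81 × 0.5 × (1/0.81 − 1) = 0.095, SE = 0.01831 and power is 78.0%.

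| Assumed loss by 3 years | Power, lost patients contribute nothing | Power, censored at a constant rate |
|---|---|---|
| 0% | 80.1% | 80.1% |
| 5% | 78.1% | 79.1% |
| 10% | 75.8% | 78.0% |
| 15% | 73.5% | 76.7% |
| 20% | 70.9% | 75.4% |

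With 10% complete loss, a truly equal procedure misses the limit in about 24% of trials (100 − 75.8) instead of 20%. Keeping 80% at that loss would take 1275/0.9 = 1417 patients.

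**4. Sensitivity to the recurrence rate.** Step 2 at other true rates, equal in both arms. The 8.2% is the figure without preoperative radiotherapy that section 4.5 cites, from a study with about 2 years of follow-up; 9% and 7% are illustrations.

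| True rate | No loss | 10% complete loss | 20% complete loss |
|---|---|---|---|
| 10% | 80.1% | 75.8% | 70.9% |
| 9% | 83.7% | 79.7% | 74.9% |
| 8.2% | 86.6% | 82.9% | 78.3% |
| 7% | 91.0% | 87.9% | 83.9% |

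**The case against.** The strongest reply is that nothing is miscalculated. Section 19.1 is right on its stated inputs, and the amount of loss is not in the protocol. Section 7 states a standard right to withdraw, which is not a forecast. One of the two exclusions in 9.3 should be rare, because section 11.1 makes biopsies mandatory. Section 10 bars exclusion for conversion or type of resection. All of this stands. A reader might infer that the protocol's own provisions imply a power of 71% to 78%. They do not: that range comes from an assumed complete loss of 5% to 20%. It is also the pessimistic version, because the log-rank analysis in 19.1 uses follow-up up to censoring.

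A second tempting step is to count every death without local recurrence as lost information and to take death rates from the colon cancer trial in section 4.3, which reports 3-year cancer-related survival of 91% and 74%. The documents do not support this. Those figures concern another disease, and section 4.3 itself urges great care in reading that trial. Deaths cost power in this way only if they are censored. In a crude proportion or a cumulative incidence, a patient who dies without recurrence has a known status and stays in the denominator. Section 19.1 does not say which estimate of the 3-year rate its interval will use.

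A third reply is that the true rate may be below 10%, in which case the loss may be offset (step 4). That limits the practical size. It does not rescue the stated 80%, because 10% is the rate on which that figure is calculated.

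**Conclusion.** The point holds as a missing allowance; the arithmetic of 19.1 is correct. The 1275 is the number of patients with known 3-year status that the formula needs, and the protocol uses it as the number to enrol. At the planning rate of 10%, any loss of information beyond the three spare patients takes power below 80%.

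The size depends on assumptions that the protocol does not supply. With an assumed 5% to 20% loss, equal in both arms, power is about 78% to 71% if lost patients contribute nothing and about 79% to 75% with constant-rate censoring. The shortfall is therefore moderate: about 2 to 4 points at an assumed 10% loss. Whether deaths add to it depends on how they enter the 3-year estimate.

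These figures assume that all patients who are not lost are followed to 3 years. Section 19.1 places the primary analysis 1.5 to 2 years after the last inclusion. That affects 3-year information separately and is not counted here.

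**What to change.** In sections 19.1 and 3.4:

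- State that 850 + 425 is the number of patients with known 3-year locoregional status that gives 80% power.
- Give the expected attrition, and say whether deaths without locoregional recurrence are censored or counted as non-events.
- Restate the power of the planned 1275 on that basis. For example, with an assumed 10% loss it is about 76% if lost patients contribute nothing and about 78% if their partial follow-up counts.

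Recruitment need not change, and no procedures are added. The cost is a wording change and a slightly less favorable stated power.

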10 RANDOMIZATION

Once eligibility has been established and patient details have been logged, the patient will be allocated to either laparoscopic or conventional operation. Randomization will be performed by computer at time of randomization. Randomization will be balanced and stratified by participating center, resection type, radiotherapy and sex. When patients are not subjected to the treatment modality as randomized, data will be analyzed on an "intention to treat basis" (once randomized, patients will not be excluded or changed groups because of conversion or type of resection).

Randomization for all centers will be done through internet:

www.color2.org (click "investigators")

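### The not-increased-recurrence claim rests on intention to treat alone, so nothing checks it against patients who receive the other operation from the start

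*Protocol*

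**What the plan says.** The aim in Protocol section 19.1 is a not-worse claim: "The primary objective of the study is to show that laparoscopic surgery does not lead to an increased locoregional recurrence rate". Equivalence is taken as shown if "the resulting two-sided 95% confidence limits of the difference in 3-yrs locoregional recurrence rates excludes a difference greater than 5" percent. The size follows from "assuming a recurrence rate of 10% in each group, 850 laparoscopic patients and 425 open patients are required to have a power of 80" percent.

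The same section then fixes the analysis set: "All analyses will be carried out on an 'intention to treat' basis", and specifically "patients, whose randomized laparoscopic operation was converted to an open resection, will be analyzed in the laparoscopic group". The summary (section 3.4) repeats the rule: "Analyses will be on 'intention to treat' basis". Section 10 applies it to patients who do not get the operation they were randomized to: "once randomized, patients will not be excluded or changed groups because of conversion or type of resection".

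The protocol names no per-protocol or as-treated analysis. Section 12.2 leaves conversion to the surgeon's discretion in general, but makes it mandatory when a positive margin is grossly visible or the tumor extends into adjacent organs. No conversion rate and no crossover rate is stated.

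**The concern.** In a superiority trial, patients who receive the other arm's treatment usually shrink the observed difference and make the trial's claim harder to reach. In a not-worse trial the same shrinkage makes the claim easier to reach. Intention to treat is therefore not automatically the cautious choice here, and a second analysis set is normally read beside it.

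Section 10 foresees patients who do not get the allocated operation, yet the wording of section 19.1 leaves no room for that second reading. If laparoscopic surgery itself raised recurrence by the full 5 points, crossover in either direction would bring the observed difference below 5. The trial would then be more likely to report no increase, and no planned result would show the reader that crossover had contributed.

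Conversions are a separate matter. They belong to the laparoscopic strategy, and their effect on the comparison may go either way.

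**Working it through.** **Inputs from section 19.1:** 10% recurrence in each group, 425 open and 850 laparoscopic patients, a 5-point limit, a two-sided 95% interval (z = 1.960).

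**Assumptions, not in the protocol:** a true rate of 15% with laparoscopic and 10% with open surgery; switched patients take the risk of the operation they received; shares switching as shown.

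**1. The plan's own figure.** For a test of the upper limit only, at 80% power and 2:1:

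n(open) = (1.960 + 0.842)² × (0.09 + 0.09/2) / 0.05² = 7.849 × 0.135 / 0.0025 = 423.8.

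This rounds to 424 open and 848 laparoscopic, 1272 in total, against 1275 in the plan. At 425/850 the standard error is √(0.09/425 + 0.09/850) = 0.01782, and the power is Φ(0.05/0.01782 − 1.960) = Φ(0.845) = 80.1%. The plan is therefore sized as a non-inferiority comparison, and the upper limit is what decides the claim.

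**2. Formula.** Let c be the share of the laparoscopic arm at open risk and x the share of the open arm at laparoscopic risk.

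- Laparoscopic-arm rate = 0.10 + 0.05(1 − c); open-arm rate = 0.10 + 0.05x
- Observed difference d = 0.05(1 − c − x)
- P(limit met) = Φ((0.05 − d)/SE − 1.960), with unpooled SE

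**3. Crossover from the start.**

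| c | x | d (points) | SE | P(limit met) |
|---|---|---|---|---|
| 0 | 0 | 5.00 | 0.01902 | 2.5% |
| 5% | 0 | 4.75 | 0.01897 | 3.4% |
| 0 | 5% | 4.75 | 0.01914 | 3.4% |
| 5% | 5% | 4.50 | 0.01909 | 4.5% |

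Last row: (0.05 − 0.045)/0.01909 − 1.960 = −1.698, and Φ(−1.698) = 4.5%.

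**4. Conversions, kept in the laparoscopic arm.** Assume 20% are converted and recur at rate h, while completed laparoscopic cases recur at 15%. The arm's rate is 0.8 × 0.15 + 0.2h.

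| h | Laparoscopic-arm rate | d (points) | SE | P(limit met) |
|---|---|---|---|---|
| 10% | 14% | 4 | 0.01880 | 7.7% |
| 15% | 15% | 5 | 0.01902 | 2.5% |
| 20% | 16% | 6 | 0.01923 | 0.7% |

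The effect changes sign at h = 15%. Below that, keeping conversions eases the claim; above it, keeping them counts against laparoscopy.

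**5. Dropping conversions instead.** Hold the laparoscopic arm at 15% overall, with 20% converted and recurring at 30%. Completed cases then recur at (0.15 − 0.2 × 0.30)/0.8 = 11.25%, so d = 1.25 points. With 680 laparoscopic and 425 open patients, SE = 0.01894 and P = Φ(0.0375/0.01894 − 1.960) = Φ(0.020) = 50.8%, against 2.5% under intention to treat. A per-protocol set that discards conversions can therefore be far more lenient than the planned analysis.

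**6. Power of a supportive set.** With 10% left out of each arm, 765 and 382 patients remain. At 10% recurrence in both, SE = 0.01879 and power = Φ(0.05/0.01879 − 1.960) = Φ(0.700) = 75.8%.

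**The case against.** The strongest reply is that the trial compares allocated strategies, and for that question intention to treat is correct and keeps its error rate. With 5% crossover each way the strategy difference really is 4.5 points, and declaring it below 5 is no error. This stands. The 4.5% describes a conclusion about the operations themselves, not a loss of the 2.5% error for the strategy comparison.

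A reader might go further and infer that keeping converted patients in the laparoscopic arm biases the trial toward its claim, pointing to the 7.7% in step 4. The documents do not support that. The figure requires converted patients to recur at the open-arm rate, while section 12.2 sends some patients with poor prognostic findings to conversion. The protocol gives neither the conversion rate nor the recurrence rate after conversion, so the sign is open.

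It can also be said that a supportive set is ordinarily left to the statistical analysis plan, which is not at hand. That has some weight. But section 19.1 speaks of all analyses, so a per-protocol analysis that appeared only in a later plan would sit at odds with the protocol.

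**Conclusion.** The point holds in a limited form. The protocol ties a not-worse claim to a single analysis set and has no check for patients operated by the other approach from the start. If the true rates are 15% and 10%, 5% crossover in one direction raises the chance of meeting the limit from 2.5% to 3.4%, and 5% in both directions raises it to about 4.5%. These shares are assumptions, and the effect is modest if crossover is rare.

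For conversions the documents fix neither size nor direction, and the planned rule is right for the strategy comparison. The tempting readings, that intention to treat is the wrong primary analysis or that the stated error rate is breached, do not follow. The sample size is not in question.

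**What to change.** Keep intention to treat as the primary analysis and add three things to section 19.1.

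- **A supportive per-protocol analysis** of the 3-year locoregional recurrence difference, with the same 95% interval and 5-point limit, in eligible patients whose operation was started by the allocated approach. Converted patients stay laparoscopic, which avoids the artefact in step 5.
- **An exploratory sensitivity analysis** that handles conversions the other way, based on the recorded conversion item (form item 38) and labelled as confounded by the reason for conversion.
- **A reporting rule:** state whether the conclusions agree, and qualify the not-worse claim if they do not.

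The cost is mainly wording, and N stays 1275. Power in the supportive set falls to about 76% if 10% are left out. The forms need one check. Item 20 records the type of resection rather than laparoscopic or open, items 36 to 39 are completed only for laparoscopic procedures, and the listed laparoscopic steps include no separate mesorectal dissection. The starting approach must therefore be confirmed as recoverable from these items and the page header. An analysis by how the dissection itself was done should not be promised.

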6 ENDPOINTS

6.1 PRIMARY ENDPOINT

- locoregional recurrence rate 3 years postoperatively

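### The only comparison named for locoregional recurrence, a log-rank test of difference, cannot decide the confidence-interval rule that defines success and gave the sample size

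*Protocol*

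**What the plan says.** The primary endpoint (Protocol 6.1) is "locoregional recurrence rate 3 years postoperatively". Section 19.1 states a no-worse aim: "The primary objective of the study is to show that laparoscopic surgery does not lead to an increased locoregional recurrence rate". It then gives a decision rule. Equivalence is shown if the "two-sided 95% confidence limits of the difference in 3-yrs locoregional recurrence rates excludes a difference greater than 5" percent. The sample size there is 850 laparoscopic and 425 open patients for 80% power, "assuming a recurrence rate of 10% in each group".

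The analysis paragraph of 19.1 names one method for this endpoint and shares it with two survival endpoints: "Locoregional recurrence rate, disease free survival and overall survival will be compared between the two procedures using log-rank statistic, adjusted for center". It names no estimator of the 3-year difference or of its interval.

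The summary in section 3.4 frames the trial differently. It opens "Using log rank statistics with a power of 80 % and a type I error of 5" percent and says that 1275 patients are needed to detect a 5% difference, with 10% recurrence in the open group. It mentions neither a margin nor a confidence interval.

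**The concern.** The success rule and the named test answer different questions. The rule asks whether an excess above 5 points at 3 years can be excluded. The log-rank test asks whether the two recurrence curves differ at all over the whole of follow-up. Its null hypothesis is equality, so a non-significant result is an absence of evidence, not evidence that laparoscopic surgery is no worse. Nor does it produce an interval on the risk-difference scale that could be set against 5 points.

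At stake is the trial's main conclusion. Someone following the analysis paragraph or the summary would report a log-rank p-value for the primary endpoint, and that p-value could be read as the answer to the no-increase question. In a sizeable share of trials this reading and the stated rule give opposite answers.

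**Working it through.** **Inputs.** From 19.1: 10% recurrence in each arm, 5-point margin, two-sided 95% interval (0.025 on the side that matters), power 80%, allocation 2:1, 850 + 425 patients. From 3.4: log-rank, 80% power, 5% type I error, 1275 patients, 10% in the open arm, 5% difference. No dropout allowance is stated, so none is used.

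**1. Which design gives 1275?**

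Non-inferiority on the risk difference:
- n(open) = [p(1−p) + p(1−p)/2] × (1.96 + 0.8416)² / 0.05² = 0.135 × 7.849 / 0.0025 = 423.8, so 424 open and 848 laparoscopic, total 1272.
- At 425/850: SE = √(0.09/425 + 0.09/850) = 0.01782. Power = Φ(0.05/0.01782 − 1.96) = 80.1%.

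This reproduces the plan's figure.

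Log-rank test of difference (Schoenfeld; events = 7.849 / [(2/9)(ln HR)²]; hazard ratio from exponential times):
- 10% vs 5%: HR = ln(0.95)/ln(0.90) = 0.487, 69 events. Average risk (0.10 + 2 × 0.05)/3 = 0.0667, so about 1035 patients.
- 10% vs 15%: HR = ln(0.85)/ln(0.90) = 1.543, 189 events. Average risk (0.10 + 2 × 0.15)/3 = 0.1333, so about 1418 patients.

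Neither gives 1275. Two-proportion tests of difference do not either (312 or 526 open patients without continuity correction, 341 or 555 with it). Nor does requiring both interval limits to lie within ±5 points (568 open). Of the designs tried, only the one-sided use of the 95% interval fits, so section 3.4 describes a design that did not produce its own sample size.

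**2. True excess at the margin (15% vs 10%, 850/425).**
- Interval rule: chance of a false pass 2.5% by construction. Simulation gave 2.3%.
- Log-rank, Schoenfeld: events = 850 × 0.15 + 425 × 0.10 = 170. Power = Φ(√(170 × 2/9) × 0.433 − 1.96) = 75.9%, so 24% non-significant.
- Two-proportion formula: pooled risk 0.1333, null SE = √(0.1333 × 0.8667 × (1/425 + 1/850)) = 0.02020, alternative SE = √(0.09/425 + 0.1275/850) = 0.01902. Power = Φ((0.05 − 1.96 × 0.02020)/0.01902) = 70.8%, so 29% non-significant.
- Simulated log-rank (exponential times, everyone followed for 3 years, no competing deaths): 30% non-significant in 4000 runs. A repeat with 20,000 runs gave 29%.

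The Schoenfeld figure is the most favourable of these to the log-rank test, so 24% to 30% is quoted as a range. Against 2.5% that is 24/2.5 = 9.6 to 30/2.5 = 12 times the intended error.

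**3. No true difference (10% in each arm).** In the same simulation the log-rank test was non-significant while the upper limit reached 5 points or more in 16.7% of 4000 runs and 16.4% of 20,000. In about one trial in six, the log-rank result would look reassuring while the plan's own rule is not met.

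**The case against.** The strongest reply is that the decision rule is already there. Section 19.1 gives the objective, the quantity, the interval, the margin and the condition for success, and its wording presupposes that an interval will be calculated. The estimator and its variance are details that a statistical analysis plan commonly holds. The log-rank sentence covers three time-to-event endpoints together and does not call itself the confirmatory test. Nowhere does the protocol say that a non-significant log-rank result shows equivalence.

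Most of that stands. A reader might infer that the plan has no valid success criterion, or that its error rate is uncontrolled. The text does not support either reading: if the interval rule is followed, the error at a true 5-point excess is 2.5%. The 24% to 30% arises only if the log-rank result replaces the rule.

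What does not stand is that this is merely detail left for later. The protocol is not silent on the analysis. It names a comparison for the primary endpoint that cannot decide its own rule, and the summary repeats that test as the basis of the design.

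A reader might also infer that analysing by intention to treat alone makes a no-worse claim too easy, because conversions dilute the laparoscopic arm. The documents do not bear this out. If, as an assumption, completed laparoscopic cases ran at 15% and 20% of operations converted at the open-arm rate of 10%, the arm's risk would be 0.8 × 15% + 0.2 × 10% = 14%. That is a true difference of 4 points, inside the margin, so a pass would be correct for the randomised strategy. Section 12.2 also mandates conversion for visible positive margins or extension into adjacent organs. Converted cases may therefore carry higher risk, and a set without them could favour laparoscopy.

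**Conclusion.** The point holds as a mismatch between a sound success rule and the only comparison named for the endpoint, made worse by section 3.4. It is not a missing rule, and the sample size is right for the rule.

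Its size is conditional. If non-significance on the log-rank test were used as proof of no increase, roughly ten times the intended share of trials would wrongly pass at a true 5-point excess. With no true difference, the two approaches would disagree in about one trial in six. These figures assume exponential recurrence times, no dropout, no competing deaths and complete 3-year follow-up. The last will not be met in full: 19.1 schedules the primary analysis 1.5 to 2 years after the last inclusion. That is a further reason to name a time-to-event estimate of the 3-year difference. Because the primary conclusion is otherwise open to two methods, the text should be corrected.

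**What to change.** In section 19.1, state that the primary analysis is the difference, laparoscopic minus open, in 3-year locoregional recurrence rates, estimated by a time-to-event method, with its two-sided 95% confidence interval. State that non-inferiority is shown if the upper limit lies below 5 percentage points. Keep the center-adjusted log-rank test as a supportive analysis for locoregional recurrence and as the comparison for disease-free and overall survival.

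Reword section 3.4 to the same design: non-inferiority by confidence interval, 10% recurrence in each group, 5-point margin, 80% power, 850 + 425 patients.

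The choice between Kaplan-Meier and competing-risk cumulative incidence, the variance and the handling of center can be left to the statistical analysis plan. The cost is wording in two sections. Sample size and data collection stay as they are.
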